14. FINANCE AND INSURANCE

Funding

This study is funded by the NIHR HSDR Programme (project reference NIHR129082). The views expressed are those of the author(s) and not necessarily those of the NIHR or the Department of Health and Social Care.

Insurance

WS1, 2 & 4 – The Institute of Cancer Research maintains Public Liability and Professional Liability insurance which will operate in this respect.

WS3 The University of Oxford maintains Public Liability and Professional Liability insurance which will operate in this respect.

Contractual arrangements

Appropriate contractual arrangements will be put in place with all third parties.

15. PUBLICATION POLICY

The Investigators will be involved in reviewing drafts of the manuscripts, abstracts, press releases and any other publications arising from the study. Authors will acknowledge that the study was funded by NIHR HS&DR. Authorship will be determined in accordance with the ICMJE guidelines and other contributors will be acknowledged.

We will seek to report results of the study both in peer-reviewed academic publications and articles written for a lay audience, e.g. writing articles for The Conversation

(www.theconversation.com). We will seek input from patient and public representatives about potential additional dissemination activities.

16. DEVELOPMENT OF A NEW PRODUCT/ PROCESS OR THE GENERATION OF INTELLECTUAL PROPERTY

Not applicable.

17. ARCHIVING

All de-identified research data and (records of) consent forms will be stored for 10 years after the end of the study. Responsible members of the University of Oxford or the Institute of Cancer Research where appropriate may be given access to data for monitoring and/or audit of the study to ensure that the research is complying with applicable regulations.

19. APPENDIX

Comparison of different alerting algorithms across five NHS hospital Trusts: Descriptive analysis of patient characteristics and frequency of process and clinical outcomes

A mainly descriptive project, with some modelling and statistical analysis, comparing groups of patients. Main cohort: patients (18+) who alerted and patients who were discharged with a SoS code (ICD-10). Time period: introduction of EHRs to March 2021.

General data description: patient information, admission & discharge information, antibiotic prescribing, microbiology tests ordered and results, ICU admission, alert details (including location of alert) Introduction

1. Background/rationale

National guidelines for screening for sepsis have been implemented in NHS Trusts. As hospitals in England introduce electronic health records, different screening algorithms have been adopted (summarised in Table 1).

		NEWS	Red Flag	SJSA	Combination*	
Trust Question re infection as part of EHR alert		UCLH	CW & RB	ICHT	OUHT	
		Yes	Yes	No	Yes	
Lungs	Respiratory rate	Yes	Yes	Yes	Yes	
	O ₂	Yes	Yes	No	Yes	
CV	Heart Rate	Yes – low & high	Yes – high only	Yes – high only	Yes – low & high	
	Blood Pressure	Yes – low & high (SBP)	Yes – low only (SBP)	Yes – low only (SBP)	Yes – low & high (SBP)	
Temperature		Yes – low & high	Amber alert – low	Yes – low & high	Yes	
Level of cor	nsciousness	Yes (VPU)	Yes (VPU)	No	Yes (VPU)	
Fluid balan	ce	No	Yes	No	No	
Lactate		No	Yes	No	Yes	
Bilirubin		No	No	Yes	No	
Creatinine		No	No	Yes	Yes	
White blood cell count		No	No	Yes	Yes	
AKI		No	No	No	Yes	

Table 1 Alert algorithms in different Trusts included in the study.

*OUHT use red flag sepsis and NEWS2

In this study we will compare the characteristics of patients who alert, the frequency of alerts across time (staff shifts, weeks and months) and patient outcomes. In addition, we will describe the completion of process measures associated with treatment of patients with sepsis. Process measures we have included are: blood cultures, lactate measure and IV-antibiotics. It is important to note that not all patients who alert will actually have clinically defined sepsis. Therefore, not all process measures will have been completed, particularly IV antibiotics. We will capture this variation in cohort and process measures across NHS Trusts.

In order to determine if differences between Trusts are algorithm dependent or intake/case mix dependent we will compare patient characteristics in those who 1) alert and 2) in those who had a discharge summary diagnosis of 'at risk of developing sepsis'. We will define those at risk of infection as those discharged with an ICD-10 code from the Suspicion of Sepsis list compiled by Inada-Kim et al.[1]

1.1 Objectives (these are the objectives in the NIHR Application)

- a) Describe the total sample of patients who are affected by the alert and baseline outcome data
- b) Describe the frequency of the alert across different Trusts, departments within Trusts and specific patient groups
- c) Describe any seasonal and temporal variations in alerts across different Trusts.
- d) Describe the impact of the Covid-19 pandemic on alerting in terms of total sample, frequency, patient demographics and seasonal/temporal variations.

2. Methods

2.1 Study design & Setting

This is a cross sectional study across five NHS Trusts in England. The period of study is 1st February 2019 to 31st January 2021, divided into two years starting 01/02/19 and 01/02/20 to consider the impact of Covid-19. The time period was selected based on the latest introduction of electronic health records across the five NHS Trusts and to separately consider patients with Covid-19 affecting the pattern of sepsis alerts.

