8. PARTICIPANT IDENTIFICATION

WS2 – Participants, Inclusion and Exclusion Criteria

Study Participants

Patients aged over 18 attending the Emergency Departments and admitted as inpatients who are included in the scope of the alert in each trust.

From the hospital population we will identify patients aged between 18 and 110 who attend the Trust and lie within the scope of the alert. The scope of the alert will vary between Trusts, for example at ICHNT patients who are attend maternity wards and outpatient clinics are not currently included in the alert scope.

Inclusion Criteria

Patients who, on discharge or death, have an ICD-10 code included in the list of codes identified as Suspicion of Sepsis used in the Sepsis Insight Dashboard [www.sos-insights.co.uk]; Patients who 'alerted' - this is a binary indicator within electronic health records, this will depend on system the Trust uses to identify patients at risk of sepsis and/or deterioration related to sepsis. In order to carry out sensitivity analysis we will extract clinical information for patients with an ICD-10 code related to a condition as identified as being appropriate to the local health economy.

Exclusion Criteria

There are no pre-registration evaluations, no specific inclusion and exclusion criteria are there is no withdrawal from the study.

WS3 – Participants, Inclusion and Exclusion Criteria

Study Participants

Participants will include hospital healthcare professionals and patients/carers in the UK. The sample size will depend on saturation³³⁻³⁴, i.e. no new themes are identified in data from later interviews/focus groups, however it is estimated that around 25 healthcare professionals and 20 patients/carers will participate.

Analysis of data from the interviews and the focus groups will occur concurrently to data collection, where possible, to inform future sampling and data collection.

Inclusion Criteria

- Participant is willing and able to give informed consent for participation in the study.
- Any gender aged 18 years or above (no upper age limit).
- Fluent in English (or able to participate in an interview with other measures in place, e.g. interpreter).
- For clinicians: Currently working as a healthcare professional (e.g. doctor, nurse) in an NHS hospital trust.
- For patients/carers: Member of the public who has previously been diagnosed with sepsis and treated in hospital or carer/relative of someone who has previously had sepsis.

Exclusion Criteria

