2.2 Participants

All adult (18+) inpatients admitted between 01/02/19 and 31/01/21 are initially eligible for inclusion in the study. We will liaise with data managers at each NHS Trust and identify all patients who triggered a sepsis alert in each Trust. The sample of patients included in the study are adult inpatients who triggered a sepsis alert at any point in their inpatient stay or time in A&E in the 24 months of the study.

The NHS Trusts included in the study are of differing sizes and may differ in case mix. In order to compare hospitals we will use patients with a serios infection, and therefore at risk of sepsis to adjust outcomes for patients with an alert. In order to identify patients with a serious infection will use the ICD-10 codes suggested by Inada-Kim et al and classed as 'Suspicion-of-Sepsis' (SoS). Patients are identified if a patient has an SoS ICD-10 code at discharge or at death.

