2.8 Missing data

Patient admissions will not be excluded if patient data is missing, an additional category of missing will be included for age, gender, ethnicity and deprivation. As part of quality checks, we will confirm whether there are any patterns in missing data, for example periods of time where no lactate were reported. Our experience of EHRs indicate that there can be periods of missing data relating to EHR downtime.

3. Statistical methods

(a) Describe all statistical methods, including those used to control for confounding

3.1 Differences in alerting over time and between patient subgroups.

We will describe the number of first alerts in each Trust in total and over different time periods. In order to compare between Trusts we will consider the number of available overnight beds as an indication of hospital size.[2]

In addition, we will compare the alerts in the ED compared to the number of consultants in the ED. We will use a Poisson model to determine if there are significant differences in alerts during different 'shifts' days of the week and seasons. The SoS admissions in the same period will be the offset in the Poisson model.

Differences in alert frequency in patient sub-groups will be assessed within and between NHS Trusts. We will use all patients discharged with an SoS diagnosis to adjust between hospitals as a case-mix adjustment.

We will describe differences in percentages of all patients and sub-groups of patients alerting between Trusts and assess the significances in differences using chi-squared tests. As there are many patient sub-groups and therefore multiple significance tests, we will use a p-value of 0.01 to assess significance. *3.2 Association between alerting and process measures*

Process measures for inclusion are IV antibiotics, blood samples taken for microbiology and lactate measurement. We will describe process measure completion in alerting patients across Trusts, and subgroups of patients including alert location, age-groups and other sub-groups. We will consider completion of individual process measures and completion of all three within three-hours.

We will model process measure completion using a logistic regression adjusted for confounding factors, primarily patient characteristics which have been identified by clinicians as clinically associated with non-completion of process measures.

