We will determine the association between the alert and completion of individual process measures, completion of the three measures, and whether the associations are different for different patient subgroups.

We will model each Trust separately and also model all patients in a multi-level model with clustering at Trust level. We will determine the sensitivity of results to the modelling approach.

Association between alerting and patient outcomes

We will assess the association between alerting and patient outcomes using a competing risks survival analysis with discharge and death as competing risks. This will allow us to fully adjust for patient factors and consider both patients who survive to discharge and those who do not. We will include process measure completion as time varying covariates.

In addition, we will separately model ICU admission after alerting using both a survival analysis and logistic model.

Association between alerting and coding

We will describe the coding of alerting patients between Trusts. The Trust which does not have a sepsis specific alert will be excluded. We determine if the differences are significant using chi-squared test. We will use descriptive approaches to compare sepsis coding between Trusts in patients with a SoS code. We will also consider whether the patterns are the same across the main patient subgroups. Statistical significance will be assessed using chi-squared tests.

(b) Methods used to examine subgroups and interactions

Within each model we will separately consider subgroups when we perform our analysis. We will consider a priori interactions.

(c) Missing data

Missing data will be included as a category on its own for factors such as ethnicity and deprivation. We will inspect data to identify periods of missing data which may be a result of EHR downtime, if necessary we will consider imputation.

We will ensure from clinicians that all process outcomes are likely to be recorded in the EHR and policy for carrying out the processes are the same across all Trusts.

Bibliography

[2] NHS Bed Availability and Occupancy Data – Overnight. Available from:

https://www.england.nhs.uk/statistics/statistical-work-areas/bed-availability-and-occupancy/bed-data-overnight/

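### Study 1's calendar split does not identify Covid-19 patients, and its 2017 Suspicion of Sepsis yardstick has no Covid-19-specific code, so SoS-scaled alert figures may shift from February 2020 for coding reasons

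*Protocol*

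**What the plan says.** All of this is in the protocol. Section 10 points to the appendix for the detailed statistical plans of WorkStream 2, so the appendix is the plan for this study.

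- **Period.** Appendix, first study, section 2.1: the 24 months are "divided into two years starting 01/02/19 and 01/02/20 to consider the impact of Covid-19". The same section gives as a reason for the period "to separately consider patients with Covid-19 affecting the pattern of sepsis alerts".
- **Objective.** Section 1.1(d): "Describe the impact of the Covid-19 pandemic on alerting in terms of total sample, frequency, patient demographics and seasonal/temporal variations".
- **Alert group.** Section 2.2: "adult inpatients who triggered a sepsis alert at any point in their inpatient stay or time in A&E in the 24 months of the study". No diagnosis condition is attached.
- **Yardstick.** Background section: "We will define those at risk of infection as those discharged with an ICD-10 code from the Suspicion of Sepsis list". The source is item [1] of that study's bibliography, "Defining and measuring suspicion of sepsis: an analysis of routine data BMJ Open 2017". Section 2.2 counts a patient as SoS if any such code is present at discharge or death.
- **Uses of the yardstick.** Section 3.1 makes SoS admissions the offset in the Poisson model of alerts by shift, day of the week and season, and adds: "We will use all patients discharged with an SoS diagnosis to adjust between hospitals as a case-mix adjustment". Table 2 gives each Trust an alert column beside an SoS column, and has a row for the proportion of alerting patients with an SoS code.
- **A second source for the list.** Section 8, WS2 inclusion criteria, takes the codes from the "list of codes identified as Suspicion of Sepsis used in the Sepsis Insight Dashboard", with no version or date.

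**The concern.** Section 2.1 states an aim at patient level and offers only a device at calendar level. After 1 February 2020 the alert group mixes Covid-19 and other patients, and nothing in the listed variables, Table 2 or the models can take them apart.

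The yardstick makes this more than a matter of wording. The background section uses the SoS comparison to judge whether differences between Trusts come from the algorithm or from the patients admitted. If a new disease enters the alert count and the SoS count in different proportions, the ratio of the two moves even when the alert treats every other patient as before. What is at stake is the reading of objective (d), of the SoS-offset seasonal results, and of between-Trust comparisons wherever Trusts carry different Covid-19 loads. A coding effect and a real change in alerting would look the same.

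**Working it through.** The protocol gives no rate or power figure for this study (section 2.6 leaves power to be determined post-hoc), so there is no stated figure to reproduce. The check has two parts.

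**1. Can Covid-19 patients enter the two groups differently?**

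- Alert group: section 2.2 has no diagnosis filter. In Table 1, respiratory rate and high heart rate are in all four alert types, and oxygen is in all but the ICHT one. The background section accepts that not everyone who alerts has clinically defined sepsis.
- SoS group: a list published in 2017 cannot hold a code specific to a disease that the plan itself places from 2020. It does not shut these patients out, because any other listed code at discharge or death admits them.

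So entry to one group depends on alerting, and entry to the other on co-coding.

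**2. What does that do to alerts per SoS admission?**

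None of the inputs below is in the documents; all are assumptions.

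- r: alerts per SoS admission in the first year
- k: non-Covid workload in the second year relative to the first, with the same r
- C: Covid-19 admissions per 100 first-year SoS admissions
- a: share of those admissions that alert
- s: share of those admissions that also carry a listed SoS code

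Second-year ratio R = (100kr + Ca) / (100k + Cs).

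R exceeds r exactly when Ca > rCs, that is when a > r × s. C and k affect the size of the shift but not its sign.

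Take k = 1, C = 20, a = 0.6. For r = 1 the numerator is 100 + 12 = 112 and the denominator 100 + 20s:

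- s = 0: 112/100 = 1.12
- s = 0.3: 112/106 = 1.057
- s = 0.6: 112/112 = 1.00
- s = 0.9: 112/118 = 0.949

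Relative change R/r - 1:

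| r | s = 0 | s = 0.3 | s = 0.6 | s = 0.9 |
|---|---|---|---|---|
| 0.5 | +24% | +17% | +11% | +5% |
| 1.0 | +12% | +6% | 0% | -5% |
| 1.5 | +8% | +2% | -4% | -8% |

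Over r = 0.5 to 1.5, k = 0.8 to 1.0, C = 10 to 20 and a = 0.3 to 0.6, the change at s = 0 is +2% to +30%. Once s is above 0 the sign is open.

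The Table 2 row for the proportion of alerting patients with an SoS code behaves in the same way. It falls if alerting Covid-19 patients carry a listed code less often than other alerting patients, and rises if more often.

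**What a flag would do.** With Covid-19 patients removed from both groups, R = 100kr/100k = r, so the coding effect is gone. With all of them counted in the SoS group, s = 1 and R = (100kr + Ca)/(100k + C). This departs from r only if a differs from r, which is a difference in alerting and not in coding. For r = 1 in the example it is 112/120 = 0.933.

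**The case against.** **A calendar split suits objective (d).** That objective concerns the pandemic's effect on alerting, and alerts in Covid-19 patients are part of that effect. This stands, and it is why a table without them should not be ranked above one with them. It does not answer section 2.1, which promises to consider the patients separately.

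**The affected comparison is partly inferred.** The Poisson model in section 3.1 names shift, day and season, with no year or pandemic term. Beds (section 3.1) and admissions or A&E attendances (section 7.2) are also scaling measures and do not depend on the SoS list. This stands as a limit: bed- or attendance-scaled counts are untouched. Seasonal and between-Trust results using SoS are still exposed, and a year-on-year use follows from objective (d) only when it is read together with the offset.

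**Entry by vital signs is not uniform.** In Table 1 three of the four alert types include an infection question, and Red Flag has temperature only as a low amber alert. This is correct, but an infection question need not screen out Covid-19, which is an infection.

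**A stronger reading is tempting.** A reader might infer that alerts per SoS admission must rise in the pandemic year by construction, and might size it as 1/(1 - c(1 - s)), with c the Covid-19 share of second-year alerts. For c = 0.1 to 0.4 and s = 0 to 0.8 that gives 1.02 to 1.67. The documents do not support this. The formula cannot fall below 1, assumes equal alert probability, and treats every non-Covid alert as coming from an SoS-coded patient, although Table 2 has a row presupposing that some alerting patients have no SoS code. Because co-coded patients do count as SoS, the shift can be nil or negative.

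**Conclusion.** The point holds in a limited form. The device in section 2.1 does not deliver its stated aim, and the SoS yardstick has no Covid-19-specific code if the published 2017 list is the one applied. SoS-scaled alert figures may therefore shift from February 2020, and differ between seasons and Trusts with different Covid-19 load, for reasons of coding.

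The size cannot be fixed from the documents. In the worked example it runs from +24% to -8%, on assumed values of r, C, a, s and k. The SoS list is not reproduced, so the co-coding share cannot be checked.

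Two list sources are cited and not reconciled. A reader might infer that their contents differ, but the documents do not say so; nor do they show whether the dashboard list holds a Covid-19 code.

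The consequence is moderate. This is a mainly descriptive study outside the primary outcome analysis, but a named objective is affected and the correction is cheap.

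**What to change.** 1. Derive a Covid-19 flag from discharge ICD-10 codes or microbiology results, both covered by the appendix's general data description for this study. Confirm at each Trust that the microbiology data carry Covid-19 results before relying on them.
2. For the year from 1 February 2020, report alert rates, the SoS-offset Poisson model and Table 2 in two versions: with flagged patients counted in both groups (in the alert group if they alerted, in the SoS group whether or not they have another listed code), and with flagged patients removed from both. Give the two equal standing.
3. Name one SoS list, with version and date, and use it throughout WorkStream 2, so that section 8 and the appendix agree.
4. Reword section 2.1 so that the calendar split is described as comparing periods and the flag as identifying patients.

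Cost: one derived variable, a second set of second-year tables, and smaller numbers in the version without Covid-19 patients.

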2.2 Participants

All adult (18+) inpatients admitted between 01/02/19 and 31/01/21 are initially eligible for inclusion in the study. We will liaise with data managers at each NHS Trust and identify all patients who triggered a sepsis alert in each Trust. The sample of patients included in the study are adult inpatients who triggered a sepsis alert at any point in their inpatient stay or time in A&E in the 24 months of the study.

The NHS Trusts included in the study are of differing sizes and may differ in case mix. In order to compare hospitals we will use patients with a serios infection, and therefore at risk of sepsis to adjust outcomes for patients with an alert. In order to identify patients with a serious infection will use the ICD-10 codes suggested by Inada-Kim et al and classed as 'Suspicion-of-Sepsis' (SoS). Patients are identified if a patient has an SoS ICD-10 code at discharge or at death.

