Aim (WS4) - Make recommendations on the effectiveness of different digital alerts and the most effective method of implementation using a systems modelling approach to assess causality of effects, including a mediation analysis (WS4)

Objectives

- 4.1. Identify the most effective digital alert for improving outcomes for patients with sepsis
- 4.2. Update our current understanding of QI implementation methodologies, with digital alerts as a specific example.
- 4.3. Identify more challenging aspects of the implementation of digital alerts in order to improve sustainability of digital interventions, if appropriate
- 4.4. Using mediation analysis, establish causal pathways between digital alert interventions and impact, incorporating qualitative and quantitative findings from WS1-3

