- Increase in *Clostridium difficile* Infections (CDI): Beta-lactam use is associated with an increased risk of acquisition of CDI, with the elderly being a group particularly at risk. We will monitor *CDI* rates within each Trust over time and investigate any changes in CDI rates following introduction of digital sepsis alerts.
- Increase in short term admissions: We will examine changes in short term admissions (<24 and <48 hours) in patients diagnosed with a bacterial infectious disease.
- Increases in administration of IV antibiotics which are deemed unnecessary. We will assess through monitoring changes in numbers of patients who are administered IV antibiotics and are discharged without a Suspicion of Sepsis or other infection code.
- Increases in the use of carbapenems and/or antibiotics from the AWaRe list²⁹ these indicators are part of the sepsis CQUIN, so will be reported by each Trust

Methods of Data Analysis

Descriptive analysis

We will summarise the number of inpatient alerts and alerts in A&Es for patients aged 18 and over in each Trust, standardised by inpatient admissions and A&E attendances respectively. As alerts can fire multiple times for one patient encounter with a hospital, we will include the first alert for each patient encounter. Simple descriptive statistics will allow us to describe variations in the numbers of alerts by Trust and, where Trusts are made up of multiple sites, by site. We will describe variation in standardised alert rates with and without taking into account patient characteristics, which will include patient age, sex and pre-existing comorbidities where this information is available. Standard statistical approaches including Chi-squared tests to determine if there are differences in the characteristics of patients across Trusts and sites. Regression models will examine seasonal variations in alert frequency and whether there are trends in standardised rates over time. We will summarise patient outcomes for each Trust based on all patients who alert and patients who received a code included in the Suspicion of Sepsis list. Where Trusts utilise the same alerting approach we will compare rates of alerts, patient characteristics and patient outcomes by alert type.

Primary analysis

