2.3 Variables

The main aim of this study is to describe and quantify differences in patients who alert in different NHS Trusts. The 'key exposure' is the algorithm used to define the sepsis alert in the five NHS Trusts. Variables of interest are identified in Table 2.

Table 2 Empty table to illustrate proposed data collection for Study 1. Superscript numbers refer to specific questions shown at the end of the document.

NHS Trust	Α		В		С		D		Е	
Sepsis alert algorithm	Red Flag	SoS	NEWS2	SoS	Red Flag	SoS	Oxford's alert	SoS	SJSA	SoS
Frequency										
Total Number of alerts in 12										
months										
Seasonal variation in alerts										
Shift (time) of alert ¹										
Patient characteristics ²										
%Male										
Age – median and IQR										
Ethnicity										
Comorbidities ³ /Conditions on										
discharge										
>Diabetes										
> Immuno-compromised										
Deprivation										
Location of alerts ⁴										
%ED										
%other key wards										
Process measures ⁵										
Received IV antibiotics										
Received IV antibiotics within 3		NA		NA		NA		NA		NA
hrs of alert										
Blood test ordered										

Blood test ordered within 3 hrs	NA	NA	NA	NA	NA
of alert.					
Lactate measurement					
Lactate measurement within 3	NA	NA	NA	NA	NA
hrs of alert					
Outcomes					
Length of stay for those who					
alert in the ED					
Admission to ICU after alert					
Mortality – 7 days					
Mortality – 30 days					
Impact on coding/formal					
diagnosis					
Proportion with a sepsis code at					
discharge/death					
Proportion with a SoS code at	NA	NA	NA	NA	NA
discharge/death					
Alert specific response	NA	NA	NA	NA	NA

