2.5 Bias

In order to compare the impact of different algorithms on the characteristics and patterns of alerting, the case-mix being admitted to the hospital is the key source of bias. All hospitals are in a similar region of England, but the intake of the five hospitals is different in terms of ethnicity, age and deprivation. In order to determine if the algorithm is the key factor determining differences in the profiles of the patients who alert we compared the profile with patients discharged with an ICD-10 SoS code.

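### Outcomes of alerting patients are compared between Trusts with an adjustment that corrects for infection intake but not for how sick a patient must be before the local algorithm fires

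*Protocol*

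**What the plan says.** All references are to the protocol; no separate SAP is at hand. In the Appendix's first (descriptive) study:

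- Section 2.2 defines the sample by the alert: "The sample of patients included in the study are adult inpatients who triggered a sepsis alert at any point in their inpatient stay" or during time in A&E. It notes that the Trusts may differ in case mix and, to compare them, states "we will use patients with a serios infection, and therefore at risk of sepsis to adjust outcomes for patients with an alert".
- Section 2.3 says the key exposure "is the algorithm used to define the sepsis alert in the five NHS Trusts". Table 2 then lists, for each Trust, an alert column and an SoS column with 7- and 30-day mortality, "Admission to ICU after alert" and length of stay for those who alert in the ED.
- Section 2.5 says that "the case-mix being admitted to the hospital is the key source of bias". Selection by the alert is not mentioned.
- Section 3.1, on alert frequency, repeats the approach: "We will use all patients discharged with an SoS diagnosis to adjust between hospitals as a case-mix adjustment".
- The outcome paragraph of section 3 adds a competing-risks model, which it expects to adjust fully for patient factors, with process measures as time-varying covariates.

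In the main text, WS4 objective 4.1 is to "Identify the most effective digital alert for improving outcomes for patients with sepsis", and section 7.4 says this will be done by integrating the findings of the earlier workstreams.

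**The concern.** The exposure decides who enters the group whose outcomes are compared. An algorithm that fires only in very sick patients yields an alerting group with high mortality. One that fires early adds many lower-risk patients and yields a group with lower mortality. This happens even if the Trusts admit the same patients and treat them identically.

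The SoS yardstick does not see this. It is defined by discharge codes, so two Trusts with the same intake and care have the same SoS mortality whatever their algorithms do. Patient-level adjustment does not close the gap either. Table 2's patient characteristics are sex, age, ethnicity, comorbidities and deprivation, and the study's general data description lists no vital signs or severity score. Lactate results are said to be in the records, but the plan uses lactate as a process measure, not as an adjustment for severity.

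At stake is whether an adjusted mortality difference between algorithms is read as a difference in care and carried into WS4.

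**Working it through.** **Nothing to reproduce.** The plan gives no alert rate, event count, sample size or power for this comparison; section 2.6 leaves power to be determined post hoc. The mechanism was therefore tested by simulation. Every rate and coefficient below is an assumption.

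**Model.** 2,000,000 patients with one intake and one standard of care, so the alert has no effect on outcome:

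- age ~ N(0,1); severity = 0.4 × age + √0.84 × N(0,1)
- logit(death) = −4.2 + 1.0 × severity + 0.3 × age
- alert score = severity + 0.6 × N(0,1); the alert fires above a threshold
- logit(SoS code) = −1.2 + 0.8 × severity, independent of the alert given severity

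Only the threshold varies. Overall mortality is 2.69%, 25.8% of patients have an SoS code, and SoS mortality is 4.39% at every threshold.

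| Alert rate | Mortality of alerters | Divided by SoS mortality | Age-standardised to SoS | SoS code among alerters | SoS patients who alerted |
|---|---|---|---|---|---|
| 5% | 11.79% | 2.69 | 9.86% | 55.2% | 10.7% |
| 10% | 9.29% | 2.12 | 8.01% | 50.3% | 19.5% |
| 20% | 6.98% | 1.59 | 6.27% | 44.5% | 34.5% |
| 30% | 5.77% | 1.32 | 5.35% | 40.7% | 47.3% |

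The last column is alert rate × share of alerters with an SoS code ÷ share of all patients with an SoS code. For example, 0.10 × 0.503 / 0.258 = 0.195.

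**What the adjustment does.** The false risk ratio for a 20% against a 10% alert is 6.98 / 9.29 = 0.75. After division by SoS mortality it is 1.59 / 2.12 = 0.75, because the same 4.39% cancels. Age standardisation gives 6.27 / 8.01 = 0.78, so most of the gap remains.

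**Sensitivity, 20% against 10%.**

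- Weaker link between severity and death (slope 0.5): 3.43 / 4.10 = 0.84; age-standardised 3.12 / 3.57 = 0.87.
- Stronger link (slope 1.5, intercept −4.8): 8.45 / 12.09 = 0.70; age-standardised 7.51 / 10.34 = 0.73.
- No link (slope 0, intercept −3.5): 3.48 / 3.59 = 0.97; age-standardised 3.23 / 3.23 = 1.00. The bias disappears, as it should.

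**A second, simpler simulation.** 4 million patients, severity X ~ N(0,1), score = X + N(0, 0.7), overall mortality 5.11% or 4.77%, and no SoS group. Comparing 30% with 10% alerting gives 9.05 / 12.50 = 0.72 (slope 0.8) and 10.15 / 15.82 = 0.64 (slope 1.2).

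**Is the needed condition met?** The bias requires that the score predicts death and that one algorithm fires at lower severity than another. The background to the Appendix's second study says such scores predict mortality strongly. Table 1 shows that the algorithms use different components and different high and low triggers.

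**Could it be mistaken for a real effect?** The 0.75 is close to the 23% reduction (ratio 0.77) that the protocol cites from one Trust. At two-sided 0.01 and 80% power, 9.29% against 6.98% would be declared different with about 3,300 alerting patients per Trust (about 1,600 with the stronger link, 19,200 with the weaker). The 0.01 level is stated for subgroup alert percentages and is used here only as an illustration.

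**After the fix.** In the same data the SoS cohort has 4.39% mortality at every threshold, a ratio of 1.00.

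**The case against.** The strongest reply is that the plan never asked the SoS adjustment to remove the threshold. The Appendix wants to separate intake from algorithm, so removing intake and leaving the algorithm visible is the intention. The study calls itself mainly descriptive, and its four objectives all begin by describing. For alert frequency and patient profile this reply stands. It does not stand for outcomes: section 2.2 prescribes an adjustment of outcomes in order to compare hospitals, section 3 models them, and section 2.5 gives the reader no warning that what remains includes selection by severity.

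Several stronger readings are tempting and are not supported:

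- *The most readily firing alert will look safest.* The protocol never uses alerter mortality to call an algorithm safe. Table 1's algorithms differ in components (infection question, lactate, bilirubin, creatinine, AKI) as well as trigger levels, so one severity axis cannot predict the real ordering.
- *The effectiveness findings as a whole are biased.* The controlled interrupted time series uses SoS-coded patients and models each Trust separately. The section 7.2 primary analysis uses controls with the same clinical characteristics. Neither has this flaw, and the route from Table 2 to objective 4.1 is possible but not spelled out.
- *Section 7.2 also plans the faulty comparison.* It does say it will "compare rates of alerts, patient characteristics and patient outcomes by alert type", but only where Trusts share an alerting approach, which is where the threshold argument is weakest.
- *The reader cannot detect the problem.* Alert rates are standardised by admissions and attendances, and SoS admissions are the Poisson offset. The share of SoS patients who alerted could be worked out from planned quantities. It is simply not tabulated.

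**Conclusion.** The point holds for the between-Trust comparison of alerting patients' outcomes in the descriptive Appendix study. SoS adjustment handles intake, and the listed factors do not measure severity, so an adjusted difference can arise from the firing threshold alone.

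The direction is firm under two conditions: the score predicts death, and one algorithm fires at lower severity than another. The size is not firm. Under the assumed alert rates of 20% or 30% against 10%, and the assumed slopes, the false risk ratio lies roughly between 0.6 and 0.85, or up to 0.87 with age standardisation and the weakest link tested. Dividing by SoS mortality is one reading of an adjustment for which the plan gives no formula.

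This is a flaw worth correcting in a mainly descriptive study. It does not undermine the project's main effectiveness analyses.

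**What to change.** In the descriptive study's sections 2.2, 2.5 and 3:

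1. State that between-Trust outcome comparisons use the SoS-coded cohort already tabulated in Table 2, adjusted for case mix. Two Table 2 rows, ICU admission after alert and length of stay for ED alerters, are defined by the alert and need an alert-free definition for that cohort.
2. Present outcomes of alerting patients as a description of who alerts. Say that they are not a comparison of algorithms and not evidence for objective 4.1.
3. Name selection by the alert threshold as a bias beside admitted case mix.
4. Add Table 2 rows for the percentage of SoS-coded and of sepsis-coded patients who alerted, next to the existing shares of alerters with those codes. In the simulation the existing SoS share moves only from 55% to 41% across thresholds, while the new one moves from 11% to 47%.
5. Add the share of all in-hospital deaths who alerted, or a check in all in-scope admissions, only if those data are extracted. The described cohort is patients who alerted or had an SoS code.

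The cost is wording and a few table rows, with no new data for items 1 to 4 as far as the described cohort shows. There are two downsides. Any effect is diluted, because not every SoS patient alerts. SoS coding may also itself be influenced by the alert, which the plan studies under coding and formal diagnosis; this should be stated as a limitation.
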